Summary of changes for Protocol version 2.2 dated 13OCT2020.

Section(s)	Changes	Rationale
Study Team	Adding [name] to the study team as key personnel. Removing [name] and [name] from the Personnel section	Personnel changes

Summary of changes: Version 2.1 Dated 23MAR2020

Sections 6.1.6, section 8.1 and section 9 have been modified to include the following statement:

“Quality of life surveys will be sent to the patients’ personal email address. Completed responses will be sent directly to our REDCAP database.”

Summary of Changes: Version 2.0 Dated 18NOV2019

1. Page 8 Hypothesis: ARM 2 boost dose was incorrect and has been changed to 4200cGY.
2. Page 6 schema had N0-1 and this has been changed to N0. This has been made consistent across the protocol.
3. Section 7.3 Treatment duration section has been revised to state that, the whole breast will be treated for five consecutive fractions for either three (Arm 1) or two (Arm 2) consecutive weeks.

[figure not shown]
Informed Consent changes:

1. The footer of the informed consent has been changed to indicate the correct version of the protocol.

No other changes have been made in the informed consent.

SCHEMA

These exams, tests or procedures are part of regular cancer care and may be done even if you do not join the study.

Protocol Summary

Full Title: Prospective Randomized study of Accelerated Radiation Therapy (PRART): a Non-Inferiority Trial to Compare Breast Cosmesis and Local Control after Concomitant Boost Breast Radiotherapy with Fifteen Fractions in Three Weeks (arm 1, standard) versus Ten Fractions in Two Weeks (arm 2, experimental)

Short Title: Randomized

Clinical Phase: Phase III

Principal Investigators: Drs. [name] and [name]

Sample Size: N= 400 (200 per Arm)

Accrual Ceiling: 430

Rate of subject accrual: Approx. 8 subjects per month or 100 patients per year

Study Population: S/p segmental mastectomy patients with Tis (DCIS), T1-T2, N0 breast cancers.

Accrual Period: 4 years

Study Design: Patients with Tis (DCIS), T1-T2, N0 breast cancers will be randomized to receive whole breast radiotherapy with a concomitant boost to the tumor bed over 15 fractions (Arm 1, standard) versus 10 fractions (Arm 2, experimental).

Study Duration: 10 years to report: 2-3 years and 5 years late toxicity, local control rate, and breast cosmesis.

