Secondary endpoints are the evaluation at 2-3 years and 5 years of fibrosis, breast cosmesis and local control. The LENT/SOMA scoring system will be used in the reporting of late radiation morbidity, including fibrosis, at baseline (prior to treatment) and at each subsequent follow-up after completing radiotherapy, scored by the research nurses assigned to the study. Breast cosmesis will be assessed using the BCTOS patient self-reports before treatment (baseline), at the end of RT, at 1-month follow up visit and at 2-year follow up visit. Local control at 2-3 years and at 5 years will be extracted from the medical record, and can be derived from clinical reports from medical, surgical or radiation oncologists as well as from the primary care doctor who is following the patient.

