1 OBJECTIVES

1. To prospectively randomize patients to one of two fractionation regimens of whole breast radiotherapy with a concomitant boost as part of breast conservation therapy in post-menopausal women with T1-2 N0 breast cancers or Stage 0 (Tis) DCIS: 4050 cGy whole breast radiotherapy with a concomitant tumor bed boost to 4800 cGy to the tumor bed in 15 fractions (Arm 1) versus 3200cGy whole breast radiotherapy with a concomitant tumor bed boost to 4200 cGy in 10 fractions (Arm 2).
2. To assess the rate of acute toxicity (grade 3 or higher).
3. To assess the rate of long-term fibrosis (grade 3 or higher) and changes in breast cosmesis in the 2 arms at 2-3 years and at 5 years.
4. To assess and compare local control at 2-3 years and at 5 years between the two arms.

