1.1 Study Hypothesis

A hypo-fractionation breast radiotherapy regimen delivered over two weeks is not inferior to standard treatment over three weeks (whole breast radiotherapy with a concomitant boost), in terms of acute toxicity and long term fibrosis, breast cosmesis and local control, at 2-3 years and at 5 years follow up.

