where α / β is a tissue dependent parameter, arising from the radiobiological linear - quadratic cell survival model.

From the randomized prospective trials, there is an estimate that breast cancer may have an alpha/beta for tumor control of 4.6 and normal breast tissue an alpha beta ratio of 3.4 [6]. The relative closeness in alpha/beta ratios of tumor and normal tissue would support a rationale for hypo-fractionation [20-23]. Based on the formula above, Table 1 includes the calculation of BEDs (biologically equivalent doses) between the 2 arms. The breast cavity is predicted to have an alfa/beta value between 3-4.

Based on Table 1 a regimen of 42 Gy in 10 fraction to the boost is comparable to 48 Gy in 15 fractions. The latter regimen has been proven to both be effective (local recurrence rate <5% at 5 years) and to be associated with excellent cosmetic results (16), justifying our choice for a biologically equivalent regimen) in the experimental arm comparable to standard arm (see α/β values in Table 1, in bold).

In view of the fact that most recurrences tend to occur at the original tumor bed and that other studies have shown efficacy of lower doses of adjuvant radiation to the rest of the breast (4-8), we elect to test a dose of 32 Gy in 10 fractions. Maintaining a relative low dose to the rest of the breast tissue, which is a much lower risk of local recurrence than the area of the tumor cavity, will reflect on very low risk of fibrosis and will enhance the likelihood of optimal breast symmetry and cosmesis.

TABLE 1

Alfa/Beta (Gy)	2 Gy x 23	2.7 Gy x 15	3.2 Gy x 15*	3.2 Gy x 10	4.2 Gy x 10*
2	46	47	62.4	41.6	65.1
3	46	46.1	59.5	39.68	60.48
4	46	45.2	57.6	38.4	57.34
10	46	42.8	52.8	35.2	49.7

- Boost Dose delivered at tumor bed

3 Staging Criteria

TNM Stage 0 (Tis N0 M0), Stage I-II, T1-2 N0 M0, newly diagnosed breast cancer patients.

4 Patient Eligibility

Inclusion criteria:

1. Women status post segmental mastectomy
2. If unilateral, pT1-2 breast cancer excised with negative margins
3. If bilateral, pT1-2 breast cancer excised with negative margins AND/OR pTis excised with negative margins.
4. Clinically N0 or pN0 or sentinel node negative
5. Ductal carcinoma in situ DCIS with negative margins (no DCIS on inked margins).
6. Women with previous contralateral breast cancer.

Exclusion criteria:

1. Previous radiation therapy to the ipsilateral breast.
2. 90 days from last surgery, unless s/p adjuvant chemotherapy

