8.1 Cosmetic results assessment

Breast cosmesis will be assessed using the Breast Cancer Treatment Outcome Scale (BCTOS) patient self-reports before treatment (baseline), at the end of RT, at 1-month follow up visit and at 2-year follow up visit. This brief self-report instrument has high reliability and validity and has been used in a variety of previous studies on recovery from breast cancer treatment. [25]. The BCTOS also will be used as a primary measure to assess breast-related symptoms and treatment effects. The receipt of the survey will be recorded by the research nurses assigned to the study, but completion is not mandatory. Quality of life surveys will be sent to the patients’ personal email address at the baseline, at the end of RT, at 1-month follow up visit and at 2-year follow up visit. Completed responses will be sent directly to our REDCAP database. The quality of life survey completion is optional.

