Time point for this questionnaire (Do not mark in this box.)

- Baseline (after consent, before randomization)

Last week of radiation therapy

45-60 days after starting radiotherapy

Two years after adjuvant radiation therapy

This form is being filled out: (Mark one.)

 By participant in doctor's office	 By clinical staff, on phone with participant
 By participant not in doctor's office	 Other

*Record the participant's study ID on each of the remaining pages
before giving the questionnaire to the participant.*

Patient Study ID

Date this questionnaire is completed:
Month Day Year

(For example, if you were completing the questionnaire on September 8, 2004, you would write 09 08 2004 in the boxes.)

Thank you for completing this questionnaire.

We are interested in your evaluation of your physical appearance and functioning since you have been treated for breast cancer. Please rate the following items on this four-point scale, according to your evaluation at this point in time.

	Difference between treated and untreated breast and area			
	None	Slight	Moderate	Large
1 Breast size	1	2	3	4
2 Breast texture (hardening)	1	2	3	4
3 Arm heaviness	1	2	3	4
4 Nipple appearance	1	2	3	4
5 Shoulder movement	1	2	3	4
6 Arm movement	1	2	3	4
7 Breast pain	1	2	3	4
8 Ability to lift objects	1	2	3	4
9 Fit of shirt sleeve	1	2	3	4
10 Breast tenderness	1	2	3	4
11 Shoulder stiffness	1	2	3	4
12 Breast shape	1	2	3	4
13 Breast elevation (how high the breast is)	1	2	3	4
14 Scar tissue	1	2	3	4
15 Shoulder pain	1	2	3	4
16 Arm pain	1	2	3	4
17 Arm swelling	1	2	3	4
18 Breast swelling	1	2	3	4
19 Arm stiffness	1	2	3	4
20 Fit of bra	1	2	3	4
21 Breast sensitivity	1	2	3	4
22 Fit of clothing	1	2	3	4

BCTOS

Patient Study ID

--	--	--	--	--	--	--	--	--	--

We are interested in your personal reactions to the surgery you have received for your breast cancer. Please answer the following questions by circling one (1) number. Please note that the response options are labeled at the end-points only. However, you can and should use all of the points on the scale as appropriate to best convey your response.

1. To what extent has your surgery **disrupted** your normal daily activities?

0	1	2	3	4	5	6	7	8	9	10
Not at all					A lot					

2. To what extent has your surgery **disrupted** your normal recreational activities?

0	1	2	3	4	5	6	7	8	9	10
Not at all					A lot					

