Patients who experience a documented cancer recurrence or second primary cancer are not expected to complete questionnaires after that event. Patients who discontinue therapy for other reasons are expected to complete all the quality of life assessments.

The first page is to be completed by a clinical staff member. Fill in the items listed on this page, print the patient's study ID at the top of pages 2 through 6 and the assessment time point at the bottom of pages 1 through 6 and give the questionnaire to the patient for completion. After the patient has completed the questionnaire, verify that the date has been recorded at the top of page 2.

Please administer the questionnaire at an office visit if possible. If that is not possible, mail the questionnaire to the patient, then call to ask for the patient's responses over the phone. If all efforts to administer the scheduled questionnaire fail, a B-39 QMD form should be submitted instead.

Institution Name / Affiliate Name

Staff Member Administering Form

Last Name

First Name

Phone

Are data amended? ☐ Yes (If yes, circle the amended items.)

This form is being filled out: (Mark one.)

- ☐ By participant in doctor's office ☐ By clinical staff, on phone with participant
☐ By participant not in doctor's office ☐ Other

Mark Circles Like This: → ●

assessment time point ☐ last week RT ☐ day 45-60 ☐ 2 years

Record the assessment time point and participant's Study ID on each of the remaining pages before giving the questionnaire to the participant.

Patient Study ID

Date this questionnaire is completed:
Month Day Year

(For example, if you were completing the questionnaire on September 8, 2004, you would write 09 08 2004 in the boxes.)

Thank you for completing this questionnaire.

We are interested in your evaluation of your physical appearance and functioning since you have been treated for breast cancer. Please rate the following items on this four-point scale, according to your evaluation at this point in time.

Difference between treated and untreated breast and area

	None	Slight	Moderate	Large
1 Breast size	1	2	3	4
2 Breast texture (hardening)	1	2	3	4
3 Arm heaviness	1	2	3	4
4 Nipple appearance	1	2	3	4
5 Shoulder movement	1	2	3	4
6 Arm movement	1	2	3	4
7 Breast pain	1	2	3	4
8 Ability to lift objects	1	2	3	4
9 Fit of shirt sleeve	1	2	3	4
10 Breast tenderness	1	2	3	4
11 Shoulder stiffness	1	2	3	4
12 Breast shape	1	2	3	4
13 Breast elevation (how high the breast is)	1	2	3	4
14 Scar tissue	1	2	3	4

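### Breast cosmesis is promised at 5 years, but no cosmesis questionnaire is scheduled after 2 years and Section 11 contains no cosmesis analysis

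*Combined protocol and SAP*

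**What the plan says.** **What is promised.** Cosmesis is in the full title. The Protocol Summary, under Endpoints, states: "Secondary endpoints are the evaluation at 2-3 years and 5 years of fibrosis, breast cosmesis and local control". Its Study Duration entry is "10 years to report: 2-3 years and 5 years late toxicity, local control rate, and breast cosmesis". Objective 3 in Section 1 covers "changes in breast cosmesis in the 2 arms at 2-3 years and at 5 years". Section 1.1 hypothesises non-inferiority in acute toxicity and in "long term fibrosis, breast cosmesis and local control, at 2-3 years and at 5 years follow up". Section 6.1.1 says that the design permits this test.

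**What is collected.** Section 8.1 designates the BCTOS self-report for cosmesis, to be completed "before treatment (baseline), at the end of RT, at 1-month follow up visit and at 2-year follow up visit". The Protocol Summary, Section 6 and the footnote to Table 4 in Section 9 give the same four occasions. The follow-up questionnaire in Section 21 offers only these boxes: "assessment time point ☐ last week RT ☐ day 45-60 ☐ 2 years". Completion is optional.

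**What is analysed.** Section 11 gives tests for acute and late toxicity, for fibrosis or telangiectasia, and for local recurrence. It does not mention cosmesis or BCTOS.

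**What the items compare.** The BCTOS column heading is "Difference between treated and untreated breast and area". Section 4 admits patients with bilateral disease and "Women with previous contralateral breast cancer". The note to Table 2 says that bilateral patients receive the assigned regimen on both sides.

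**The concern.** A time point that is named in the hypothesis, objectives, endpoints and reporting plan has no scheduled measurement behind it. A patient's rating of her breast at 5 years cannot be recovered later from the chart, unlike a recurrence. If nothing changes, the trial reaches its 5-year report with one part of its stated hypothesis unanswerable. The alternative would be a substitute measure chosen after the data are known.

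The 2-year data have a related weakness. Non-inferiority in cosmesis is hypothesised, but no score, margin, model or rule for missing forms is fixed in advance. Any choice would therefore be made late in the trial.

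**Working it through.** No stated figure is at issue, so the check is to set promised time points against scheduled measurements.

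| Secondary endpoint | Promised at | Source at 2-3 years | Source at 5 years |
|---|---|---|---|
| Fibrosis | 2-3 and 5 years | LENT/SOMA (Sections 8.1.1, 9) | LENT/SOMA (Section 9 names 5 years) |
| Local control | 2-3 and 5 years | Medical record (Section 9) | Medical record (Section 9 names 5 years) |
| Cosmesis | 2-3 and 5 years | BCTOS at 2 years | None |

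**Count of BCTOS administrations.** Four are scheduled: baseline, end of radiotherapy, 1 month and 2 years. One lies in the 2-3 year window, at its lower edge. None comes after 2 years, so none is at 5 years.

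**Does Table 4 rescue it?** The BCTOS row has a plain X under post-treatment follow-up, which alone could mean every visit. The footnote attached to that row lists the four occasions and ends at 2 years.

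**Does another form rescue it?** The Excellent/Good/Fair/Poor rating sits on the same questionnaires, whose last time-point box is 2 years. The missing-data form in Section 22 also ends at 2 years.

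**Is the study too short for a 5-year survey?** The inputs are from the Protocol Summary: 400 patients, a ceiling of 430, about 8 per month or 100 per year, and a duration of 10 years.

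- Planned pace: 400 / 100 = 4.0 years of accrual, and 4.0 + 5 = 9.0 years to the last 5-year visit.
- Slowest reading: 8 × 12 = 96 per year, 430 / 96 = 4.48 years, and 4.48 + 5 = 9.48 years.

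Both fit within 10 years. The gap lies in the assessment schedule, not in the length of the study.

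**Analysis.** Section 11 sets a non-inferiority margin only for acute toxicity (5 percentage points above 10%). No margin or test is given for cosmesis. Baseline BCTOS is collected and objective 3 speaks of changes, so the data for a baseline-adjusted analysis exist, but the plan does not say that they will be used.

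**The case against.** The best defence is that some information on appearance will exist at 5 years. LENT/SOMA scores retraction or atrophy, telangiectasia and pigmentation, and it is recorded at each follow-up. That is true, and it would be wrong to say that nothing on breast appearance is collected. But the protocol designates these nurse-scored items as late morbidity and assigns cosmesis to the patient's own report, so they are a proxy at most.

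It is also fair that cosmesis is a secondary endpoint. The sample size rests on acute toxicity, and optional completion is not in itself a defect: the appendix forms already provide for phone or mail follow-up and for recording missing questionnaires.

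Three stronger readings are tempting, and the documents do not support them.

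- *Patients without an untreated reference breast bias the trial towards non-inferiority.* They are randomised to both arms. Items without a clear reference may dilute a difference, but they may also add variance, which widens the interval and makes non-inferiority harder to show. With no cosmesis margin, neither effect can be judged.
- *Such patients are numerous.* Their share is not given. The criterion on previous contralateral cancer came only with version 6.0 in October 2024. Two months later the ceiling was raised from 420 to 430 because of withdrawals, which suggests that accrual was well advanced. Bilateral patients remain a valid question.
- *The 2-year comparison will be unadjusted, with a calculable loss of precision.* Section 11 names no cosmesis analysis at all, and objective 3 points to change from baseline. There is no stated comparator, and no correlation between baseline and follow-up scores from which to compute a loss.

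**Conclusion.** The point holds. Cosmesis at 5 years is an endpoint, an objective, part of the non-inferiority hypothesis and a planned report, yet the number of scheduled patient-reported cosmesis assessments at 5 years is zero. Separately, no cosmesis analysis is specified for any time point.

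The first conclusion rests on reading the Table 4 footnote as limiting its row, which agrees with every other statement of the schedule. The second rests on the absence of any cosmesis entry in Section 11. Neither needs a numerical assumption.

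The reference-breast issue is a question of interpretation that merits a sensitivity analysis; it is not a demonstrated bias. The effect is confined to a secondary endpoint: the primary test and the sample size stand as they are on this point.

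**What to change.** 1. **Reconcile the schedule, one way or the other.** Either add a 5-year BCTOS survey, by the e-mail and REDCap route already in use, to the Protocol Summary, Sections 6, 8.1 and 9, the Table 4 footnote and the time-point boxes of the follow-up form. Or limit cosmesis to 2 years in the endpoints, objective 3, the hypothesis, Section 6.1.1 and the planned reporting.
2. **Specify the analysis in Section 11.** Name the BCTOS items that form the cosmetic score, since the 22 items also cover arm and shoulder function. Compare the arms on that score, adjusted for baseline BCTOS. State a margin if non-inferiority in cosmesis is to be claimed; otherwise report the difference with its confidence interval and do not call it a non-inferiority result.
3. **Add a sensitivity analysis** that excludes patients with bilateral treatment or a previously treated contralateral breast. Define these groups by status at randomisation, so that the comparison between arms stays randomised.

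**Cost.** A short amendment and, under the first option, one more optional survey per patient. Version 1.0 is dated November 2019 and version 7.0 December 2024. The enrolment start is not given, so the earliest patients may already have passed 5 years and the 5-year data may be incomplete. The report should give the number surveyed and the number responding by arm. Whether the consent covers a further survey cannot be judged, because the consent pages are not in the material available. Limiting the claim to 2 years costs nothing in data collection but gives up the 5-year cosmesis result. Neither option changes the sample size.

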1 OBJECTIVES

1. To prospectively randomize patients to one of two fractionation regimens of whole breast radiotherapy with a concomitant boost as part of breast conservation therapy in post-menopausal women with T1-2 N0 breast cancers or Stage 0 (Tis) DCIS: 4050 cGy whole breast radiotherapy with a concomitant tumor bed boost to 4800 cGy to the tumor bed in 15 fractions (Arm 1) versus 3200cGy whole breast radiotherapy with a concomitant tumor bed boost to 4200 cGy in 10 fractions (Arm 2).
2. To assess the rate of acute toxicity (grade 3 or higher).
3. To assess the rate of long-term fibrosis (grade 3 or higher) and changes in breast cosmesis in the 2 arms at 2-3 years and at 5 years.
4. To assess and compare local control at 2-3 years and at 5 years between the two arms.

1.1 Study Hypothesis

A hypo-fractionation breast radiotherapy regimen delivered over two weeks is not inferior to standard treatment over three weeks (whole breast radiotherapy with a concomitant boost), in terms of acute toxicity and long term fibrosis, breast cosmesis and local control, at 2-3 years and at 5 years follow up.

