3. 60 days from last chemotherapy
4. Male breast cancer

5 Descriptive Factors/Stratification/Randomization Scheme

This is a prospective, randomized study. No stratification is planned. The study schema describes the study design.

5.1 Study Schema /Table 2

Eligibility	Stage 0 or Stage I-II breast cancer s/p segmental mastectomy.	
Day 0	Informed consent and randomization CT planning for determination of tumor bed on the prone position	
Days 1-15 (start within 90 days from last breast surgery)	Weekly IGRT, IMRT or Conformal breast irradiation, randomly assigned to: 15 fractions whole breast radiotherapy with concomitant boost (arm 1) or 10 fractions whole breast radiotherapy with concomitant boost (arm 2)	
Note: Patients with bilateral breast cancer will be randomized to receive the same dose and fractionation to both breasts		

6 Treatment plan

6.1.1 The women in this study will be randomly assigned to receive either 10 or 15 radiation fractions. The study design permits to test non inferiority of the 2 weeks versus 3 weeks regimen in terms of acute toxicity, fibrosis, breast cosmetic results and local control at 2-3 years and at 5 years follow up.

6.1.2 The informed consent process is as follows. The principal investigator explains all elements of the protocol to the patients and answers any and all questions. Clinical procedures are performed by the principal investigator. The research nurse will obtain blood sample by venipuncture. The consent process takes place in the Department of Radiation Oncology at Weill Cornell Medical Center. The consent form process is concluded when the patient, principal investigator and the witness all have signed the consent form. The witness is a present adult able to verify that the patient was given the proper information needed to make an informed decision to participate in the clinical study. year 1

6.1.3 Once the process of randomization is concluded, patients will be informed of the schedule based on the assigned one of the 2 arms.

6.1.4 Simulation and treatment will be started within 90 days from surgery, in order to maximize the chances of optimal lumpectomy cavity visualization on the planning and cone beam CT scans.

6.1.5 Our routine follow up is once a year after completion of radiation therapy. For the purpose of protocol significance (for assessment of fibrosis), we will require at least one follow up visit to our department, after years 2. (See 11.1 Study calendar).

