11 STATISTICAL AND DATA MANAGEMENT CONSIDERATIONS

Study Design: This study is a prospective randomized controlled trial to test the hypothesis that whole breast radiotherapy to 3200cGy with a concomitant tumor bed boost to 4200 cGy in 10 fractions (Arm 2,) is not inferior to standard whole breast radiotherapy with a concomitant tumor bed boost to 4800 cGy to the tumor bed in 15 fractions (Arm 1).

A total of 400 patients will be randomized to arm 1 or 2 to test the primary hypothesis that the proportion of patients with grade ≥ 2 acute toxicity with 2 weeks regimen would not be $> 5\%$ greater than the rate of 10% with a standard 3weeks regimen, with a 1-sided α of 0.025 and power of 79%.

The trial will have 2 planned interim analyses at 80 patients (20%; rejecting the null hypothesis when $Z \leq -4.88$, or $P \leq 0$) and at 240 patients (60%; rejecting the null hypothesis when $Z \leq -2.67$, or $P \leq 0.0038$) and a final analysis at 400 patients (100%; rejecting the null hypothesis if $Z \leq -1.98$, or $P \leq 0.0238$). The secondary objective was to test whether a significant difference exists between the 2 arms for long term fibrosis or telangiectasia grade ≥ 2 . The secondary objective has 1 planned interim analysis when 50% of the patients had completed 3 years of post-treatment follow-up (rejecting the null hypothesis if the hazard ratio was ≤ 0.37 , or $P < 0.0031$) and a final analysis when all the patients

had completed 3 years of follow-up (rejecting the null hypothesis if the hazard ratio was ≤ 0.63 , or $P < 0.049$).

The distributions of the baseline patient and disease characteristics at randomization for each arm will be summarized using descriptive statistics. Quantitative variables were summarized using the means, standard deviations, medians, and ranges; qualitative variables were summarized with frequency distributions of the nominal levels. Wilcoxon rank sum tests were used to compare the distributions of the quantitative variables between the 2 arms, and Fisher exact tests were used to compare the distributions of the qualitative variables between the 2 arms.

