To summarize the safety data, distributions of toxicity grades will be provided by treatment arm. Noninferiority tests will be conducted to test the primary hypothesis that the 2 weeks regimen would result in no more toxicity than did the 3 weeks regimen. Fisher exact tests will be used to compare the distributions of acute and late toxicity grades between the 2 weeks arm and the 3 weeks arm.

The comparison of the cumulative incidence of long term fibrosis or telangiectasia grade ≥ 2 between the 2 arms will be conducted using log-rank χ^2 tests. The hazard ratio between the 2 arms will be computed with the 95% confidence intervals.

Local recurrence-free survival will be estimated for both treatment arms using Kaplan-Meier curves, the relative risk will be estimated, and the 2 arms will be compared using the log-rank χ^2 tests.

11.1 Data management:

Data Management will be carried out by staff of the Department of Radiation Oncology at WCMC under the direction of [name]. Randomization will occur from a randomization list provided by [name]'s team and allocation to each arm will be performed, after consent is acquired, by the research team in the department of Radiation Oncology. The Randomization will be a manual process where the data manager will enter the consented patient's name in a sequential order in the Randomization list provided. Data will be entered into the JCTO Clinical database management system maintained by the JCTO according to the procedures of WCM. Patients will be followed every 12 months to evaluate their status with respect to recurrence. Recurrences will be evaluated using standard criteria in the Dept. of Radiation Oncology that are provided in the protocol. Data will be transferred from the Clinical database to the Division of Biostatistics for analysis. The Principal Investigator, Research Nurse and Data Manager have access to data collected.

Analysis: Patient characteristics at randomization will be summarized by treatment group using descriptive statistics and graphical displays.

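### Non-inferiority is claimed for fibrosis, cosmesis and local control, but only acute toxicity has a margin and a non-inferiority test

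*Combined protocol and SAP*

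**What the plan says.** **The claim.** The title describes "a Non-Inferiority Trial to Compare Breast Cosmesis and Local Control". The hypothesis in the Protocol Summary and in Section 1.1 is wider: the two-week regimen is not inferior "in terms of acute toxicity and long term fibrosis, breast cosmesis and local control, at 2-3 years and at 5 years follow up". Section 6.1.1 makes it a statement about the design: "The study design permits to test non inferiority of the 2 weeks versus 3 weeks regimen in terms of acute toxicity, fibrosis, breast cosmetic results". The same sentence also names local control at 2-3 and 5 years.

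**The analysis (Section 11).**
- *Acute toxicity, grade 2 or higher:* the experimental rate is to be no more than 5 points "greater than the rate of 10% with a standard 3weeks regimen"; the test is planned "with a 1-sided α of 0.025 and power of 79"%. Non-inferiority tests are planned for this primary hypothesis and for nothing else.
- *Fibrosis or telangiectasia, grade 2 or higher:* "The secondary objective was to test whether a significant difference exists between the 2 arms". The test is log-rank, and a hazard ratio with a 95% interval is reported. The null is rejected at a hazard ratio of 0.37 or less (P < 0.0031) at the interim and 0.63 or less (P < 0.049) at the final analysis, when all patients have 3 years of follow-up.
- *Late toxicity grades:* Fisher exact tests.
- *Local control:* "Local recurrence-free survival will be estimated for both treatment arms using Kaplan-Meier curves, the relative risk will be estimated", with a log-rank comparison. No margin, event target or power is given.
- *Cosmesis:* no analysis appears. The Protocol Summary and Sections 6, 8.1 and 9 place the BCTOS at baseline, end of radiotherapy, 1 month and 2 years, and completion is not mandatory.

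**The concern.** A non-inferiority conclusion needs a margin fixed in advance and a confidence limit that excludes it. A test of no difference offers neither. When it is non-significant it says only that the data did not separate the arms, and with few events that is a common result even when one arm is materially worse.

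The stated aim (Section 2.2) is to try to establish a new standard of care, so the late outcomes will carry weight. Local control is the sharpest case because recurrences will be few. Table 1 gives Arm 2 a lower whole-breast equivalent dose (39.68 against 46.1 at alpha/beta 3). The protocol explains this as deliberate, and the tumor-bed values are nearly equal (60.48 against 59.5). The table is no evidence of harm; it shows why an excess in recurrence should be bounded and not merely left undetected.

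**Working it through.** **1. The plan's own late-outcome figures.** No sample size, event count or power is stated for fibrosis, cosmesis or local control. The fibrosis boundaries do show what kind of test was planned. With equal arms, the events at which a hazard ratio sits exactly on its P value are D = 4 × (z / ln HR)².
- Interim: HR 0.37, two-sided P 0.0031, z = 2.96, giving D = 35.4.
- Final: HR 0.63, two-sided P 0.049, z = 1.97, giving D = 72.6.

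This is about 36 and 73 events, a 50%/100% split. O'Brien-Fleming-type spending at two-sided 0.05 gives P values of 0.0031 and 0.049, as stated. These are the boundaries of a two-sided test of HR = 1, not of a non-inferiority test.

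**2. What 73 fibrosis events can show.** At an observed HR of 1, the upper 95% limit is exp(1.96 × 2/√73) = 1.58. With a true HR of 1.5, power is Φ(ln 1.5 × √73/2 − 1.97) = Φ(−0.24) = 0.41, so the result is non-significant about 59% of the time.

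**3. Local control.** Section 2.3 says the 15-fraction regimen "has been proven to both be effective (local recurrence rate" below 5% at 5 years). I take 5% as the ceiling. The 3% and 2% rates are my assumptions, used to show the range. All rows assume 200 patients per arm and complete 5-year follow-up.

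With equal true rates p:
- events D = 400p
- half-width of the 95% interval = 1.96 × √(2p(1−p)/200)
- upper HR limit at observed HR 1 = exp(1.96 × 2/√D)

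| Rate in both arms | Events | Half-width (points) | Upper HR limit |
|---|---|---|---|
| 5% | 20 | 4.3 | 2.4 |
| 3% (assumed) | 12 | 3.3 | 3.1 |
| 2% (assumed) | 8 | 2.7 | 4.0 |

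If recurrence truly doubles from p1 to p2:
- HR = ln(1−p2)/ln(1−p1)
- D = 200(p1 + p2)
- power = Φ(ln HR × √D/2 − 1.96)

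| True rates | HR | Events | Power | Non-significant |
|---|---|---|---|---|
| 5% vs 10% | 2.05 | 30 | 0.505 | about 50% |
| 3% vs 6% (assumed) | 2.03 | 18 | 0.324 | about 68% |
| 2% vs 4% (assumed) | 2.02 | 12 | 0.23 | about 77% |

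Loss to follow-up would lower the event counts and worsen these figures.

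**4. Would adding a margin rescue the claim?** The documents give none, so these are assumed: one-sided 0.025, equal true rates, 200 per arm. Power for local control is:

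| Control rate | Margin 2 points | Margin 3 points | Margin 5 points |
|---|---|---|---|
| 5% | 15% | 28% | 63% |
| 3% | 21% | 42% | 83% |
| 2% | 30% | 57% | 95% |

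Power reaches 80% only with a 5-point margin on a low rate. That would accept 8% against 3% (2.7-fold) or 7% against 2% (3.5-fold).

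**5. Cosmesis.** Nothing can be computed, because Section 11 gives no BCTOS summary measure, standard deviation or margin. At 5 years there is no BCTOS assessment to analyse.

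**The case against.** The best defence is that the plan already ranks its outcomes. Acute toxicity is the sole primary endpoint and the late outcomes are secondary. Objectives 3 and 4 in Section 1 speak only of assessing and comparing. Section 11 is open that the fibrosis test looks for a difference, and it already plans a hazard ratio with a 95% interval for fibrosis, and Kaplan-Meier curves and a relative risk for local recurrence. Much of this stands. The primary test is untouched, and part of the estimation asked for is already there. But secondary status does not supply a margin, and the title, the hypothesis and Section 6.1.1 still make the claim.

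Three stronger readings are tempting, and the documents do not support them.
- *That the plan will declare non-inferiority from a non-significant test.* No section says so. The risk is that a reader could draw that conclusion, because Section 6.1.1 promises a non-inferiority answer and tests of difference are the only late-outcome comparisons planned.
- *That all three late outcomes are tested by log-rank, or that the title claims all four outcomes.* Log-rank covers fibrosis/telangiectasia and local recurrence only. The title names only cosmesis and local control.
- *That Table 1 shows Arm 2 to be under-dosed.* The lower whole-breast value is explained in Section 2.3, and the tumor-bed values are close at alpha/beta 3 and 4 (60.48 against 59.5; 57.34 against 57.6).

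It is also fair to say that at the 5% ceiling a missed doubling is an even chance. It becomes the more likely result only at lower, assumed rates.

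**Conclusion.** The concern holds. The documents claim non-inferiority on outcomes for which they set no margin and plan no non-inferiority test, so the Section 6.1.1 statement about the design is wrong as written. For cosmesis there is no planned analysis at all, and the 5-year claim has no data source.

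For local control, the trial at the documents' 5% ceiling could not exclude a 2.4-fold hazard even with identical observed results, and it would miss a true doubling about half the time. These figures rest on 400 patients with complete 5-year follow-up and proportional hazards. The 3% and 2% rows rest on assumed rates. The fibrosis figures rest on the 73 events inferred from the stated boundaries.

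This should be fixed. It changes what may be concluded about the late outcomes, not the validity of the primary comparison.

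**What to change.** 1. In the title, the hypothesis (Protocol Summary and Section 1.1) and Section 6.1.1, limit the confirmatory non-inferiority claim to acute toxicity. The title now names only cosmesis and local control, so both would be replaced as the outcomes claimed.
2. In Section 11, report fibrosis and local control at 2-3 and 5 years as arm differences (cumulative incidence or Kaplan-Meier difference, and hazard ratio) with 95% intervals.
3. Add an analysis of cosmesis: BCTOS change from baseline at 2 years, as an arm difference with a 95% interval, with the number of completed questionnaires per arm.
4. Remove the 5-year cosmesis claim, since the BCTOS is not collected then.
5. Add to Section 11: *a non-significant log-rank or Fisher test will not be interpreted as non-inferiority*.

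The alternative is to set and justify a margin for each late outcome and judge it by the confidence limit. On the figures above, this sample size would support that for local control only with a wide margin and a low event rate.

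The cost is a protocol amendment and a more modest claim. No new patients or data are needed.
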